8.3.1.2. BIOBADASER

Baseline characteristics captured by BIOBADASER are collected from the recruiting clinician or directly from each patient enrolled in the register using an electronic standardized form. The variables to be captured by the register are summarized in the following section.

Patient Baseline Characteristics

Baseline variables will include the following:

- Age (at baseline)
- Sex
- Renal impairment
- Date of initiation of filgotinib
- Initial dose of filgotinib
- First ever administration of filgotinib: y/n
- Previous RA treatment immediately prior to initiation of filgotinib
- Date of diagnosis of RA (year)
- Current severity of RA
 - Disease Activity Score (DAS):
 - DAS for 28 joint count (DAS28)
 - DAS28 type: ESR; CRP
 - CRP value
 - ESR value
 - VAS (patient assessment of disease)
 - RA type (seropositive, seronegative)
 - Date of assessment

Risk Factors for MACE, VTE, and Serious and Opportunistic Infections

As previously described, each registry was assessed for the availability of the set of potential risk factors for the 3 endpoints of concern.

Table 4 Risk Factors for MACE, VTE and Serious and Opportunistic Infections as Available in BIOBADASER

	MACE	VTE	Serious and Opportunistic Infections
History of CVD	Yes		
History of VTE		Yes	
Previous serious infection			Yes
Age	Yes	Yes	Yes
Sex	Yes		
Diabetes	Yes		Yes
Chronic kidney disease (stages 4, 5)	Yes		Yes
Smoking	Yes	Yes	
Hyperlipidemia	Yes		
Hypertension	Yes		
Active cancer & history of cancer		Yes	
Recent hospitalization		Yes	
Recent surgery		Yes	
Known thrombophilic condition		Yes	
Ongoing hormonal replacement therapy		Yes	
Heart and/or respiratory failure		Yes	
Acute myocardial infarction or ischemic strokes		Yes	
Obesity or BMI		Yes	
Acute infection and/or rheumatologic disorder		Yes	
Chronic lung disease			Yes

	MACE	VTE	Serious and Opportunistic Infections
Prior DMARD treatment failure			Yes
Glucocorticoid			Yes
TNFi			Yes

BMI = body mass index; CVD = cardiovascular disease; DMARD = disease-modifying antirheumatic drug; MACE = major adverse cardiovascular event; TNFi = tumor necrosis factor inhibitor; VTE = venous thromboembolism

Physician Adherence

In accordance with the RMP, SmPC and the description provided in Section 6.2, the following variables will be used to describe the adherence of the prescribing physician with respect to the Guide for HCP.

- Diagnosis of TB: yes/no
 - Date of diagnosis
- Diagnosis of herpes zoster: yes/no
 - Date of diagnosis
- Diagnosis of viral hepatitis: yes/no
 - Date of diagnosis
- Patient is currently pregnant: yes/no
 - Weeks pregnant
- Date of most recent full term pregnancy (for women aged < 50 years old)
- The patient is suffering from a serious and opportunistic infection (as defined by MedDRA): yes/no
 - Infection type
 - Date of diagnosis

Dose and age are already variables for this study and thus the use of 100 mg in patients aged ≥ 75 years old and in patients with chronic kidney disease can be addressed.

- Screening:
 - TB
 - Date of screening
 - Result of screening test

Concomitant Medication

- Concomitant use of other immunosuppressant:
 - Type, name, and dose (where recorded)

Additional Variables: Laboratory and Counselling

BIOBADASER is the only registry that can supplement their data through additional data collection screens based on clinical practice. The additional variables are summarized below.

Table 5 Additional Variables in BIOBADASER

Variable			
ANC (neutrophils)	Value	units	Date
ALC (lymphocytes)	Value	units	Date
Hb	Value	units	Date
HDL	Value	units	Date
LDL	Value	units	Date
Total cholesterol	Value	units	Date
triglycerides	Value	units	Date
HDL:LDL	Value	units	Date
Advice given on contraceptive use	y/n		
Advice given on spermatogenesis	y/n		
Advice given on breast feeding	y/n		

ALC = absolute lymphocyte count; ANC = absolute neutrophil count; Hb = hemoglobin; HDL = high density lipoprotein; LDL = low density lipoprotein

8.3.1.3. BSRBR-RA

Patient Baseline Characteristics

Baseline variables will include the following:

- Age (at baseline)
- Sex
- Renal impairment
- Date of initiation of filgotinib
- Initial dose of filgotinib
- First ever administration of filgotinib: y/n
- Previous RA treatment immediately prior to initiation of filgotinib

- Date of diagnosis of RA (year)
- Current severity of RA
 - DAS:
 - DAS for 28 joint count (DAS28)
 - DAS28 type: ESR; CRP
 - CRP value
 - ESR value
 - HAQ score
 - VAS (patient assessment of disease)
 - RA type (seropositive, seronegative)
 - Date of assessment

Risk Factors for MACE, VTE, and Serious and Opportunistic Infections

A set of variables will be collected at baseline to define the risk of each of the 3 outcomes of concern: MACE, VTE, and serious and opportunistic infections (see definitions in Section 6.1 and Annex 4).

As previously described, each registry was assessed for the availability of the set of potential risk factors for the 3 endpoints of concern.

Table 6 Risk Factors for MACE, VTE and Serious and Opportunistic Infections as Available in BSRBR-RA

	MACE	VTE	Serious and Opportunistic Infections
History of CVD	Yes		
History of VTE		Yes	
Previous serious infection (partial availability)			Yes
Age	Yes	Yes	Yes
Sex	Yes		
Diabetes type 1	Yes		Yes
Diabetes type 2	Yes		Yes
Atrial fibrillation	Yes		
Chronic kidney disease (stages 4,5)	Yes		Yes
Smoking	Yes	Yes	

	MACE	VTE	Serious and Opportunistic Infections
Hyperlipidemia	Yes		
Hypertension	Yes		
Cancer and date of diagnosis		Yes	
Ongoing hormonal replacement therapy		Yes	
Acute myocardial infarction or ischemic strokes		Yes	
Obesity or BMI		Yes	
Chronic lung disease			Yes
Glucocorticoid			Yes
TNFi			Yes
Other immunosuppressant/modifying treatment			Yes

BMI = body mass index; CVD = cardiovascular disease; MACE = major adverse cardiovascular event; TNFi = tumor necrosis factor inhibitor; VTE = venous thromboembolism

Physician Adherence

In accordance with the RMP, SmPC and the description provided in Section 6.2, the following variables will be used to describe the adherence of the prescribing physician with respect to the Guide for HCP.

- Diagnosis of active TB: yes/no
 - Date of diagnosis
- Diagnosis of herpes zoster: yes/no
 - Date of diagnosis
- Diagnosis of viral hepatitis: yes/no
 - Date of diagnosis
- Previous opportunistic infection: yes/no
 - Date of diagnosis: yes/no
- Pregnancy: yes/no

Dose and age are already variables for this study and thus the use of 100 mg in patients aged ≥ 75 years old and in patients with chronic kidney disease can be addressed.

- Screening:

- TB
- Date of screening
- Result of screening test
- Record of recent administration of herpes zoster (live attenuated) vaccine:
 - Date

Concomitant Medication

- Concomitant use of other immunosuppressant:
 - Type, name, dates and dose

8.3.1.4. DANBIO

Patients are reported to the database at the time of diagnosis, referral to specialized treatment, including biological therapy at the hospital, or in a private rheumatologic clinic. At the first registration, the diagnosis, date of diagnosis, and other disease related variables (including previous DMARD treatments, anti-cyclic citrullinated peptide, and immunoglobulin M rheumatoid factor status, disease activity measures), socio demographic factors (age, sex), and health behavioral factors (including tobacco use) are registered.

The variables for the study will be collected at baseline; this is the date of each patient's first prescription/administration of filgotinib in the observational period. These variables reflect the patient's status at baseline (initiation of filgotinib) or the medical history prior to and including the baseline date. The variables to be captured by the register are summarized in the following section.

Patient Baseline Characteristics

Baseline variables will include the following:

- Age (at baseline)
- Sex
- Renal impairment
 - Current stage (1 to 5)
- Date of initiation of filgotinib
- Initial dose of filgotinib
- First ever administration of filgotinib: y/n
- Previous RA treatment immediately prior to initiation of filgotinib
- Date of diagnosis of RA (year)
- Current severity of RA
 - DAS28 CRP
 - HAQ score
 - VAS (patient assessment of disease)
 - RA type (seropositive, seronegative)

- Date of assessment

Risk Factors for MACE, VTE, and Serious and Opportunistic Infections

As previously described, each registry was assessed for the availability of the set of potential risk factors for the 3 endpoints of concern. With regards to serious and opportunistic infections, it is worth noting that DANBIO developed a risk score for infection (Krabbe et al., 2021). The risk factors considered are age, previous serious infection, pulmonary disease, diabetes and myocardial infarction and glucocorticoid use within the last year.

Table 7 Risk Factors for MACE, VTE and Serious and Opportunistic Infections as Available in DANBIO

	MACE	VTE	Serious and Opportunistic Infections
History of CVD	Yes		Yes
History of VTE		Yes	
Previous serious infection			Yes
Age	Yes	Yes	Yes
Sex	Yes		
Diabetes type 1	Yes		Yes
Diabetes type 2	Yes		Yes
Atrial fibrillation	Yes		
Smoking	Yes	Yes	
Hyperlipidemia	Yes		
Hypertension	Yes		
Active cancer & history of cancer		Yes	
Known thrombophilic condition		Yes	
Reduced mobility / Hospitalization (date, type, length of stay)		Yes	
Trauma and/or surgery		Yes	

	MACE	VTE	Serious and Opportunistic Infections
Ongoing hormonal replacement therapy		Yes	
Heart and/or respiratory failure		Yes	
Acute myocardial infarction or ischemic strokes		Yes	
Obesity or BMI		Yes	
Acute infection and/or rheumatologic disorder		Yes	
Chronic lung disease			Yes
Prior DMARD treatment failure			Yes
Glucocorticoid			Yes
TNFi			Yes
Other immunosuppressant/modifying treatment			Yes

BMI = body mass index; CVD = cardiovascular disease; DMARD = disease-modifying antirheumatic drug; MACE = major adverse cardiovascular event; TNFi = tumor necrosis factor inhibitor; VTE = venous thromboembolism

Physician Adherence

In accordance with the RMP, SmPC and the description provided in Section 6.2, the following variables will be used to describe the adherence of the prescribing physician with respect to the Guide for HCP.

- Diagnosis of TB: yes/no
 - Date of diagnosis
- Diagnosis of herpes zoster: yes/no
 - Date of diagnosis
- Diagnosis of viral hepatitis: yes/no
 - Date of diagnosis
- Patient is currently pregnant: yes/no
 - Weeks pregnant
- Date of most recent full term pregnancy (for women aged <50 years old)
- The patient is suffering from a serious and opportunistic infection (as defined by MedDRA): yes/no
 - Date of diagnosis

Dose and age are already variables for this study and thus the use of 100 mg in patients aged ≥ 75 years old and in patients with chronic kidney disease can be addressed.

Concomitant Medication

- Concomitant use of other immunosuppressant (csDMARDs, prednisolone):
 - Type, name, and dose
 - Dates of prescriptions

8.3.1.5. RABBIT

This study will make secondary use of prospectively collected existing data in the RABBIT registry. Baseline data captured in RABBIT are collected by the recruiting physicians using a standardized form.

Patient Baseline Characteristics

Baseline variables will include the following:

- Age (at baseline)
- Sex
- Renal impairment
- Date of initiation of filgotinib
- Initial dose of filgotinib
- First ever administration of filgotinib: y/n
- Previous RA treatment immediately prior to initiation of filgotinib
- Date of diagnosis of RA (year)
- Current severity of RA
 - Disease Activity Score (DAS):
 - DAS for 28 joint count (DAS28)
 - DAS28 type: ESR; CRP
 - CRP value
 - ESR value
 - HAQ (from FFbH Hannover) score
 - RA type (seropositive, seronegative)
 - Date of assessment

Risk Factors for MACE, VTE, and Serious and Opportunistic Infections

As previously described, each registry was assessed for the availability of the set of potential risk factors for the 3 endpoints of concern.

Table 8 Risk Factors for MACE, VTE and Serious and Opportunistic Infections as Available in RABBIT

	MACE	VTE	Serious and Opportunistic Infections
History of CVD	Yes		
Age	Yes	Yes	Yes
Sex	Yes		
Diabetes	Yes		Yes
Chronic kidney disease	Yes		Yes
Smoking	Yes	Yes	
Hyperlipidemia	Yes		
Hypertension	Yes		
Active cancer		Yes	
Hospitalization (date, type, length of stay)		Yes	
Surgery		Yes	
Heart and/or respiratory failure		Yes	
Acute myocardial infarction or ischemic strokes		Yes	
Obesity or BMI		Yes	
Acute infection and/or rheumatologic disorder		Yes	
Chronic lung disease			Yes
Prior DMARD treatment failure			Yes
Glucocorticoid			Yes
TNFi			Yes
Other immunosuppressant/modifying treatment			Yes

BMI = body mass index; CVD = cardiovascular disease; DMARD = disease-modifying antirheumatic drug; ; MACE = major adverse cardiovascular event; TNFi = tumor necrosis factor inhibitor; VTE = venous thromboembolism

Physician Adherence

In accordance with the RMP, SmPC and the description provided in Section 6.2, the following variables will be used to describe the adherence of the prescribing physician with respect to the Guide for HCP.

- Diagnosis of TB: yes/no
 - Date of diagnosis
- Diagnosis of herpes zoster: yes/no
 - Date of diagnosis
- Diagnosis of viral hepatitis: yes/no
 - Date of diagnosis
- Patient is currently pregnant: yes/no
 - Weeks pregnant

Dose and age are already variables for this study and thus the use of 100 mg in patients aged ≥ 75 years old and in patients with chronic kidney disease can be addressed.

- Record of recent administration of vaccines:
 - Date and type of vaccine (live attenuated; inactivated, mRNA; subunit type; toxoid, viral vector)
- Screening (at baseline and every 2.5 years):
 - TB
 - Viral hepatitis

Concomitant Medication

- Concomitant use of other immunosuppressant:
 - Type, name, date and dose

8.3.2. Variables to be Collected During Patient Follow-up

The variables to be collected during the follow-up which will describe endpoints (see Section 6.2) related to aRMMs adherence are provided in the following table. These therefore include pregnancy, use of vaccines and lipid monitoring. Monitoring of TB following the initial screening for latent disease is not included: firstly, testing is not required and; secondly, evaluating whether clinicians routinely check for signs and symptoms is not be feasible via registry data.

As well as the occurrence of the variables, appropriate dates will be collected. Furthermore, the patients' index dates, end of treatment and end of follow-up dates will be used to estimate the exposure time.

Table 9 Availability of Endpoints to Assess Adherence by Registry During Patient Follow-up

Follow-up Variable	ARTIS	BIOBADASER	BSRBR-RA	DANBIO	RABBIT
Pregnancy	Yes	Yes	Yes	Yes	Yes
Dx of incident TB	Yes	Yes	Yes	Yes	Yes
Viral hepatitis	Yes	Yes	Yes	Yes (only history)	Yes
Administration of live attenuated vaccine	No	Yes	Yes (HZ only)	No	Yes
Lipid monitoring (approx.. 12 weeks after initiation of filgotinib)	No	Yes	No	No	No

Dx = diagnosis, HZ = herpes zoster, TB = tuberculosis

In addition to the above variables, the occurrence of a VTE event whilst the patient is using filgotinib will be identified and specifically the subsequent treatment pattern occurring such as discontinuation of filgotinib will be recorded.

8.4. Data Sources

8.4.1. ARTIS

SRQ and ARTIS

A description of ARTIS is provided in Section 6.2. Details of data linkage is provided below. Furthermore, SRQ also provides disease activity information, which is measured by CRP, ESR, HAQ, number of swollen and tender joints, and patient's global assessment of disease (on a VAS) and physician's evaluation on a Lickert type scale. In addition, DAS28, the European League Against Rheumatism (EULAR) response criteria, and the American College of Rheumatology criterion of improvement (American College of Rheumatology 2050) can be calculated.

Data entry into SRQ is provided by the patient and the rheumatologist in conjunction with visits. Visits are scheduled according to treatment guidelines and clinical practice, which means at 0, 3, and 6 months after the initiation of a new antirheumatic therapy, and thereafter in relation to the level of disease activity according to an overall treat-to-target paradigm. A Swedish prescription is valid for 1 year, which contributes to patients in remission also being seen regularly. The treating physicians enter the results into the study database via a web-based interface. Optionally, it is possible to send the data to the study secretariat on a predesigned paper form. Patients can enter their data through internet ahead of the visit, at touchscreens in the waiting room, or on paper.

A) Swedish Nationwide Register Linkages

The register linkage has many advantages in providing data on all comorbidities that have been diagnosed. Importantly, it also allows for obtaining data on comparator cohorts, so that any potential risk increases can be evaluated considering risks among patients with other treatments, and the general Swedish population. The drawback is a lag time of between 1 to 2 years from when an event occurs until it can be analyzed and reported using the registries.

B) The Swedish Patient Register and the Prescribed Drug Register

The Swedish Patient Register collects information on all hospitalized (inpatient-treated) patients, and all visits to nonprimary outpatient care (such as a visit to a rheumatologist). Diagnoses are assigned by the treating/discharging physician, as well as date of discharge, discharging hospital, and department. Diagnoses are coded according to the International Statistical Classification of Diseases and Related Health Problems (ICD), with Version 8 used until 1986, Version 9 from 1987 to 1996, and Version 10 since 1997. The inpatient component was originally initiated by several counties in 1964, had 85% countrywide coverage in 1983, and is considered complete since 1987. Validation against medical files have found an overall error rate in the main diagnoses of 4% at the ICD chapter level, and 12% at the 3-digit level. The outpatient component of the Swedish Patient Register was initiated with nationwide coverage in 2001. Overall, 13% of outpatient visits lack records, but coverage is higher for somatic public care (including most rheumatology care). Chart reviews and validation of the RA diagnosis based on different algorithms applied to the register data indicate a positive predictive value for a register-based diagnosis of RA around 90% (S. Eriksson et al., 2013; Knight et al., 2008).

C) The Swedish Cancer Register

The Swedish Cancer Register was established in 1958 and contains information on date of cancer (and some selected precancers) onset, and type of cancer according to the ICD classification and morphology/histology. Approximately 99% of cancers have been morphologically verified. Reporting of incident cancers (including invasive malignancies as well as cancer in situ) is mandatory and semiautomated, resulting in an estimated coverage greater than 95% (Barlow et al., 2009; Mattsson & Wallgren, 1984).

D) The Medical Birth Register

The Medical Birth Register contains prospectively provided data from antenatal, obstetric, and neonatal records since 1973, and covers all live and still births (but not all miscarriages) in Sweden. Among the variables covered are maternal age, parity, smoking and family situation in early pregnancy, and the infant's birth weight and length, gestational age (primarily based on ultrasound dating), and Apgar score. Complications and mother's and infant's morbidities are coded according to the ICD, with Version 8 used until 1986, Version 9 from 1987 to 1996, and Version 10 since 1997.

E) The Cause of Death Register

The Cause of Death Register is a national register containing information on date and cause of death (underlying and contributory) for all deceased residents, including deaths among Swedish residents who died abroad. The register was started in 1952, and the data are considered complete since 1961. From that year and onward, cause of death is missing for less than 0.5% of deceased individuals, and in 2002, a validation study estimated that only 3.3% had any errors at the 3digit level of the ICD-coded underlying cause of death.

F) The Total Population Register

The Total Population Register was founded in 1961 and lists data on residency at a given point in time, and dates of emigration/immigration for all subjects ever residing in Sweden since 1961. This register will be used to identify the general population comparison cohorts, and to censor subjects who die or emigrate during follow-up.

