8.3.1.1. ARTIS

Patient Baseline Characteristics

Baseline variables will include the following:

- Age (at baseline)
- Sex
- Renal impairment
 - Stage (if available)
- Date of initiation of filgotinib
- Initial dose of filgotinib
- First ever administration of filgotinib: y/n
- Previous RA treatment immediately prior to initiation of filgotinib
- Date of diagnosis of RA (year; approximate if greater than 10 years earlier)
- Current severity of RA
 - Disease Activity Score (DAS):
 - DAS for 28 joint count (DAS28)
 - DAS28 type: Erythrocyte Sedimentation Rate (ESR); C-reactive protein (CRP)
 - CRP value
 - ESR value
 - Health Assessment Questionnaire (HAQ) score
 - Visual analogue scale (VAS; patient assessment of disease)
 - RA type (seropositive, seronegative)
 - Date of assessment

Risk Factors for MACE, VTE, and Serious and Opportunistic Infections

As previously described, each registry was assessed for the availability of the set of potential risk factors for the 3 endpoints of concern. In ARTIS there are no measures of obesity or immobility, both risk factors for VTE, although HAQ could be used as a proxy.

Table 3 Risk Factors for MACE, VTE and Serious and Opportunistic Infections as Available in ARTIS

	MACE	VTE	Serious and Opportunistic Infections
History of cardiovascular disease	Yes		
History of VTE		Yes	
Previous serious infection			Yes
Age	Yes	Yes	Yes
Sex	Yes		
Diabetes type 1	Yes		Yes
Diabetes type 2	Yes		Yes
Atrial fibrillation	Yes		
Chronic kidney disease	Yes		Yes
Smoking	Yes	Yes	
Family history CVD	Yes		
Use of treatment: Hyperlipidemia (Dx unavailable)	Yes		
Use of treatment: Hypertension (Dx unavailable)	Yes		
Cancer diagnosis (date)	Yes	Yes	Yes
Known thrombophilic condition		Yes	
Reduced mobility / Hospitalization (date, type, length of stay)		Yes	
Trauma and/or surgery		Yes	

	MACE	VTE	Serious and Opportunistic Infections
Ongoing hormonal replacement therapy		Yes	
Heart and/or respiratory failure		Yes	
Acute myocardial infarction or ischemic strokes		Yes	
Chronic lung disease			Yes
Glucocorticoid			Yes
TNFi			Yes
Other immunosuppressant/modifying treatment			Yes

CVD = cardiovascular disease; Dx = diagnosis; MACE = major adverse cardiovascular event; TNFi = tumor necrosis factor inhibitor; VTE = venous thromboembolism

Physician Adherence

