8.4.4. DANBIO

In DANBIO, data are captured electronically from the source, requiring only little instruction of the patients and health care professionals. DANBIO has developed dedicated touch screens (and from home access) where patients enter data on, for example, disability, pain, lifestyle, and health-related quality of life, in the waiting room or from home. During the consultation, nurses, rheumatologists, and other healthcare professionals add data on, for example, joint counts and medications on their computers.

The validity of the RA diagnosis in DANBIO, is >80%, and has been described elsewhere (Hallager et al., 2017). Registrations of medications (exposure) are prospectively validated at department level as part of the annual quality report. It is estimated, by DANBIO, that the overall error rate is < 5% for the Anatomical Therapeutic Chemical level. For outcomes, these are captured through linkage with national administrative registries, which are virtually complete. The error rate varies between outcomes and is estimated to be <5% at the ICD-10 chapter level and <10% at the 3-digit level.

In addition, DANBIO will link registry patients to national health and demographic registers in Denmark for additional data.

A) The Civil Registration System (CRS) of Denmark

Since 1968, each person residing in Denmark is given a unique identification number, the central person registration (CPR) number, which serves as a key reference to the individual in all public registers (Pedersen, 2011; Pedersen et al., 2006). The CPR number is used to link individual data from the registers.

B) The Danish National Patient Register (DNPR)

The register contains data on all hospital contacts since 1976. The data available today includes inpatient hospitalization, emergency room visits, outpatient hospital visits, admission and discharge dates, all surgical procedures, and all diagnosis codes. The diagnoses are based on international classification of disease, Version 10 (ICD 10 codes).

C) The Danish National Database of Reimbursed Prescriptions

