The Danish health care system provides partial reimbursement of almost all prescription medications in Denmark. Since 2004, information on all reimbursed prescriptions has been gathered in the Danish National Database of Reimbursed Prescriptions. Medication administration in hospitals is not registered by CPR numbers, and this information can therefore not be used for individual level analyses. The medicinal products are classified according to the World Health Organization Anatomical Therapeutic Classification System (ATC) coding system (Pottegård et al., 2017; Sørensen et al., 1995; Sørensen & Larsen, 1994).

D) Statistics Denmark

Statistics Denmark (<http://www.dst.dk>) was established in 1850. The institution collects detailed socioeconomic information on all Danish inhabitants regarding education, occupation, economics, etc., has a copy of the national health registers; and makes the data available for research.

E) The Danish National Register of Causes of Death

Since 1875, the National Board of Health has maintained this register of deaths among Danish inhabitants dying in Denmark, and since 1970 the records have been computerized. From 1994, the classification of cause of death was based on ICD 10 codes (Helweg-Larsen, 2011). Data are made available for research by electronical access to a pseudonymized data copy via a safe and password protected data portal at the Danish Health Data Authority (<https://sundhedsdatastyrelsen.dk>), or at Statistics Denmark (above). Besides the public registers, there is a range of clinical databases available for register-based research.

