
Hyperlipidemia
	
BIOBADASER: Lipid measures LDL, HDL, total cholesterol or triglycerides may be captured according to clinical practice.
	
Patients who will initiate treatment with statins and other lipid-lowering drugs.

	
BSRBR-RA: Patients who will initiate treatment with statins or other lipid-lowering drugs.
 
RABBIT: Hyperlipidemia reported as adverse event by the treating physician.
	
--	--	--

Other medical history

Disease	Data source	ICD10
Malignancy	The Cancer register	All except benign tumors
Infection	Main diagnoses from the Inpatient component of Patient Register.	A00B99, D73.3, E06.0, E32.1, G00G02, G04.2, G05G07, H00.0, H44.0, H60.0H60.3, H66H67, H70, I30.1, I40.0, J00J22, J32, J34.0, J36, J38.3, J39.0J39.1, J44.0, J85, J86, K04.4, K04.6, K04.7, K10.2, K11.3, K12.2, K14.0, K57.0, K57.2, K57.4, K57.8, K61, K63.0, K65.0, K65.1, K65.2, K65.9, L00L08, L30.3, M00M01, M46.2M46.5, M60.0, M65.0, M71.0, M71.1, M72.6, M86, N10, N11, N12, N13.6, N15.1, N15.9, N30.0 N30.8, N34.0, N41.2, N43.1, N45.2, N45.3, N45.4, N48.2, N61, N70, N73, N75.1
Renal impairment		N18, N18.1, N18.2, N18.3, N18.4, N18.5
Knee or hip prosthesis	Operation codes from the Patient register	NGB, NFB
Diabetes	The Patient Register	E10E14, O24
Myocardial infarction	The Patient Register	I21, I22

SIGNATURE PAGE – INVESTIGATOR

Study Title: Non-interventional post-authorization cohort safety study evaluating the effectiveness of the additional risk minimization measures for filgotinib (Jyseleca®) use in patients with moderate to severe active rheumatoid arthritis within European registries

CSP Version:

1.0

Date:

02-Feb-2022

I, the undersigned, have read this non-interventional study protocol and will conduct the study as described in compliance with the study protocol, in accordance with the guidelines of Good Pharmacoepidemiology Practises and Heads of Medicines Agencies Good Pharmacovigilance Practices.

Investigator Name

Signature

Date

SIGNATURE PAGE – SPONSOR

Study Title: Non-interventional post-authorization cohort safety study evaluating the effectiveness of the additional risk minimization measures for filgotinib (Jyseleca®) use in patients with moderate to severe active rheumatoid arthritis within European registries

CSP Version: 1.0 **Date:** 02-Feb-2022

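### Annex 4 takes diabetes only from Patient Register codes (E10-E14, O24), so some diabetics in ARTIS and, by inference, DANBIO are scored non-diabetic in the MACE and infection risk profiles

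*Protocol*

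**What the plan says.** The general claim for ARTIS is in Section 8.4.1, part A: "The register linkage has many advantages in providing data on all comorbidities that have been diagnosed". Part B then describes the Swedish Patient Register as covering inpatients and "all visits to nonprimary outpatient care (such as a visit to a rheumatologist"), and adds: "Overall, 13% of outpatient visits lack records, but coverage is higher for somatic public care".

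For DANBIO, Section 8.4.4 says of the Danish National Patient Register: "The register contains data on all hospital contacts since 1976". It lists "inpatient hospitalization, emergency room visits, outpatient hospital visits, admission and discharge dates, all surgical procedures, and all diagnosis codes".

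The diabetes definition is a single row in the Other medical history table of Annex 4: "Diabetes The Patient Register E10E14, O24". It gives no second source. Table 3 (ARTIS) and Table 7 (DANBIO) each list type 1 and type 2 diabetes as risk factors for MACE and for serious and opportunistic infections.

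Drug data appear elsewhere in the protocol:
- Table 3 has the entry "Use of treatment: Hypertension (Dx unavailable") and a matching entry for hyperlipidemia.
- The ARTIS/DANBIO column of Annex 4 defines hyperlipidemia by lipid-lowering treatment.
- A heading in Section 8.4.1 names the Prescribed Drug Register, and Section 8.3.1.1 lists dispensing dates for concomitant immunosuppressants.
- For Denmark, Section 8.4.4 says that since 2004 "information on all reimbursed prescriptions has been gathered in the Danish National Database of Reimbursed Prescriptions".

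**The concern.** The sentence in Section 8.4.1 promises more than the registers described after it can give. Neither register is described as including primary care. A patient whose diabetes was never coded at a hospital or specialist contact is counted as not having it. Table 3 itself concedes that diagnoses of two other chronic conditions are unavailable and falls back on treatment, but diabetes has no such fallback.

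O24 is the code for diabetes in pregnancy. It includes gestational diabetes, which is neither of the two types listed in Tables 3 and 7, so a past gestational-only episode would count as diabetes.

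The first objective in Section 7 is at stake. Diabetes feeds two of its three high-risk proportions, MACE and serious or opportunistic infection.

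**Working it through.** **The protocol's own precision figure.** Section 8.5 takes a 10% high-risk proportion with 300 users. SE = √(p(1−p)/n) = √(0.10 × 0.90 / 300) = 1.73%. The interval is 10% ± 1.96 × 1.73% = 6.6% to 13.4%. Both match the stated values.

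**Inputs not in the documents (assumed).**
- d, true diabetes prevalence among starters: 5-15%.
- s, share of diabetics with a qualifying register code: 50-90%.
- g, share of non-diabetics with a gestational-only O24 code: 0-1%.
- u, share of diabetics who are at high risk through diabetes alone: 10-100%.

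**Step 1: recorded diabetes** = d·s + (1−d)·g. With d = 10% and g = 0, the register shows 5.0%, 7.0% or 9.0% at s = 50%, 70% or 90%. With g = 1%, each rises by 0.90 × 1% = 0.9 points, to 5.9%, 7.9% or 9.9%.

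**Step 2: direction.** At d = 5%, s = 90% and g = 1%, recorded diabetes is 4.5% + 0.95% = 5.45%, slightly above the true 5%. The undercount dominates in most of the assumed range, but not in all of it.

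**Step 3: loss in the high-risk proportion, before O24** = d·(1−s)·u.

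| Case | d | s | u | Loss (points) |
|---|---|---|---|---|
| Smallest | 5% | 90% | 10% | 0.05 × 0.10 × 0.10 = 0.05 |
| Middle | 10% | 70% | 30% | 0.10 × 0.30 × 0.30 = 0.9 |
| Largest | 15% | 50% | 100% | 0.15 × 0.50 × 1.00 = 7.5 |

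The middle case is 0.9 / 1.73, about half of the standard error in Section 8.5. That standard error rests on an illustrative 300 users, not on an expected ARTIS or DANBIO count.

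**The case against.** The best reply is that capture may be good.
- Section 8.2.1 says Swedish RA patients are typically treated by rheumatologists, mostly in public hospital-based clinics, and those visits fall inside the register.
- The Infection row of the same table is limited to main inpatient diagnoses. The Diabetes row is not, so a secondary code at any specialist or hospital visit is enough. A reader might infer that all diabetes managed in primary care is lost. The text does not support that: only patients never coded in covered care are missed.

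The attribution to DANBIO is also an inference. The Other medical history table names no registry, although its source names match the ARTIS/DANBIO column of the main Annex 4 table.

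Three stronger readings fail.
- A reader might divide missed diabetes cases by the 1.7-point standard error. With prevalence of 8-12% and 50-80% capture, 1.6 to 6.0 points are missed, which looks like 1 to 3.5 standard errors. That standard error belongs to the high-risk proportion, and a missed diabetic changes that proportion only if no other listed factor already qualifies the patient. Age, smoking, cardiovascular history and glucocorticoids are among those factors.
- A reader might conclude that ARTIS and DANBIO will look lower risk than the registries that use forms. Section 8.9 says recorded history can depend on the professional and on patient memory, so forms may under-record too. The study is descriptive, and the protocol plans no formal comparison between registries.
- A reader might say the code range forces types 1 and 2 to be pooled. A range in an annex does not prevent reporting them separately.

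Section 8.9 also mentions endpoint misclassification and uneven data capture, but not this gap. What stands after all this is an over-broad sentence and a single-source definition with drug data named for both countries.

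**Conclusion.** The point holds as a definitional weakness of uncertain size. Diabetics never coded in inpatient or specialist outpatient care (Sweden) or at a hospital contact (Denmark, if the row applies there) are scored as non-diabetic. This contradicts the completeness claim in Section 8.4.1. O24 adds a probably small error in the opposite direction.

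The effect on the first objective cannot be fixed from the protocol, which gives no rule for combining risk factors into high-risk status. The range of 0.05 to 7.5 points, with a middle case of about 0.9, rests wholly on the assumed prevalence, capture and diabetes-alone shares, and it is before any O24 offset. It shows that the effect could be negligible or could exceed the illustrated sampling error. It is not an estimate of bias.

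**What to change.** In Annex 4, name the registries to which the Other medical history table applies. For ARTIS and DANBIO, define diabetes as either of these:
- an E10-E14 code at or before the index date;
- a dispensing of a glucose-lowering drug (ATC A10) in the 12 months before the index date, taken from the Swedish Prescribed Drug Register or the Danish reimbursed-prescription database.

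This follows the treatment-based approach that ARTIS already takes for hyperlipidemia and hypertension. Drop O24 as a stand-alone criterion, and report the code-only figure as a sensitivity line so that the contribution of the drug data is visible. In Section 8.4.1, limit the linkage sentence to comorbidities diagnosed in inpatient or specialist outpatient care.

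The cost is some Annex 4 wording and a few lines of code on sources the protocol already names. The downside is that a few users of A10 drugs who do not have diabetes will be counted.
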